6.3.3 Time to Cessation of Ventilator Support

Start and stop time for mechanical ventilation will be documented in EDC.

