#### **9.2.4 Time to cessation of ventilator support**

Based on data from subjects on O2 support at baseline, the probability of time to cessation of ventilator support will be calculated via Kaplan-Meier based on ordinal scale data. Time to cessation of ventilator support will be calculated as Date of Event – Date of Day 1. If the event is not achieved then the value will be censored and calculated as Date of the last available ordinal assessment – Day 1. P-values for each VIS410 dose versus placebo, VIS410 total versus placebo and for VIS410 4000 mg versus 2000 mg will be presented. Results will be presented graphically as well.

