#### **9.2.5 Healthcare resource utilization**

Descriptive statistics will be used to compare the total number of days in the hospital and/or ICU from admission to discharge, number of subjects requiring ICU admission post-randomization, overall number of days in the ICU, number of hours on ventilation, rehospitalization due to influenza A relapse/reinfection, the total number of days of oseltamivir therapy, and the total number of days to resumption of usual activities by treatment group.

Time (number of days) to resumption of usual activities will be determined from the VAS (scale ranged from 0 to 10, where 0 indicates subject is unable to perform any of his/her usual activities prior to influenza onset, and 10 indicates subject is able to fully perform all usual activities). Time to resumption of usual activities will be calculated as the difference between the first day the subject reports a score of 10 and Day 1. If a subject does not report a score of 10 by Day 14, a value of 14 will be used in the analysis. This evaluation will be performed using the MITT population. Additional analyses of VAS scores will reflect summaries of mean VAS scores by study day (up to Day 14), along with change from baseline and percent change from baseline will be generated; p-values will be based on ANOVA using rank transformation of VAS scores. VAS summaries will also be generated in the subsets of subjects with time from onset of symptoms to treatment < 72 hours or ≥ 72 hours. Mean VAS scores by study day along with standard deviations will be presented in figures, overall subjects and in the indicated subsets.

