-  During hospitalization, body temperature will be recorded at the end of infusion on Day 1 then BID up until Day 14 or discharge from the hospital if discharge occurs prior to Day 14. In cases where obtaining oral temperature is not possible, core temperature will be obtained. While hospitalized, the maximum temperature should be recorded for each 12-hour interval (from 12 AM to 12 PM and from 12 PM to 12 AM).
-  Additional targeted physical exam may be performed throughout the study as needed at the Investigator's or his/her designee's discretion.
-  The Influenza Patient Reported Outcomes (FluPRO) Questionnaire (Appendix 14.1) must be completed (ie, self-reported) by the subject at baseline (Day 1) and daily thereafter through Day 14. Subjects who are not able to complete the questionnaire at baseline (Day 1) will be exempt from this assessment throughout the study. The FluPRO will be completed at home for subjects that are discharged from the hospital prior to Day 14.
-  The ordinal scale will be completed from baseline (Day 1) and daily thereafter through Day 14. For each day, subjects will be classified by the worst clinical outcome for which they qualify.
-  A urine or serum pregnancy test must be performed at screening locally (ie, by the investigative site) within 2 days prior to dosing. Negative results must be obtained prior to randomization.
-  A serum pregnancy test will be performed at the central lab for all female subjects of childbearing potential following randomization at baseline.
-  Subjects to be enrolled based on the Investigator's discretion including any local laboratory results per SOC at institution.
-  See Laboratory Assessments for list of tests to be performed by the Central Lab in Appendix 14.2.
-  Serum creatinine to be done locally within 24 hours prior to randomization, the result is required for oseltamivir dosing.
- 20a ESR to be performed locally.
-  A chest x-ray or computed tomography (CT) scan taken per SOC within 72 hours before dosing is acceptable.
-  Healthcare utilization (total length of hospital stay, length of ICU stay, and rehospitalization) will be captured through the last follow-up visit.

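### SAP 9.2.4 times ventilator cessation from the once-daily ordinal score, which ends at Day 14, although ventilation stop times are recorded in EDC for this endpoint

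*SAP*

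**What the plan says.** For this endpoint, SAP 9.2.4 states that "the probability of time to cessation of ventilator support will be calculated via Kaplan-Meier based on ordinal scale data". The time unit is a difference of dates: "Time to cessation of ventilator support will be calculated as Date of Event – Date of Day 1". For censoring: "If the event is not achieved then the value will be censored and calculated as Date of the last available ordinal assessment – Day 1".

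The SAP's schedule of assessments (16.2) fixes what that source can show: "The ordinal scale will be completed from baseline (Day 1) and daily thereafter through Day 14", and "For each day, subjects will be classified by the worst clinical outcome for which they qualify".

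The protocol provides a finer source. Section 6.3.3, whose heading is the name of this endpoint, consists of one sentence: "Start and stop time for mechanical ventilation will be documented in EDC". Protocol 10.6.4 plans Kaplan-Meier estimates and log-rank tests for the endpoint. It names no ordinal source and sets no Day 14 limit. Follow-up per subject runs to about Day 56 (Protocol 4.2).

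The SAP expects ventilation data finer than a daily score. Section 9.2.5 summarises "number of hours on ventilation" descriptively, and the planned listings have a ventilator-support listing (16.2.6.3) separate from the ordinal-scale listing (16.2.6.6). SAP 16.1, which lists departures from the protocol's analyses, does not mention the ordinal derivation. No analysis of this endpoint on the recorded stop times is planned.

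**The concern.** Times collected under this endpoint's own heading are replaced, with no stated reason, by a coarser and shorter proxy in the only ventilation analysis that produces curves and p-values. A subject who comes off the ventilator in the morning is still scored as ventilated that day. A subject who comes off in the third week has no event.

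The study is exploratory and not powered for this endpoint (SAP 2.2). Its stated purposes are to rank candidate Phase 3 endpoints by strength of evidence and, per the protocol synopsis, to supply estimates for powering them. A curve that runs late and stops at 13 days serves both purposes less well. If more than half of an arm is still ventilated when the score ends, that arm's median cannot be estimated.

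**Working it through.** The documents give no event count, ventilation duration or power for this endpoint, so there is no stated figure to reproduce. The check derives what the SAP rule records and compares it with the true stop time.

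**Inputs from the documents:** one score per day, Days 1 to 14, worst status of the day; time = event date minus Day 1 date; censoring at the last ordinal assessment; follow-up to Day 56.

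**Assumptions:** infusion at mid-Day 1 (f = 0.5); exponential ventilation times; no deaths; the event is the first day scored off the ventilator (SAP 9.2.4 does not say which score change marks it).

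**Last observable stop.** A stop on Day d is still scored as ventilated on Day d. The first ventilator-free score is on Day d + 1, so the recorded time is (d + 1) − 1 = d days. It is seen only if d + 1 ≤ 14, that is d ≤ 13. The longest censoring time is 14 − 1 = 13 days.

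**Delay.** Let t be the true time from infusion in days and c = f + t, so d = floor(c) + 1. The excess is d − t = f + (d − c), with d − c between 0 and 1. For f = 0.5 it lies between 0.5 and 1.5 days; simulation gave a mean of 0.99.

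**Stops that become censored.** A stop is unseen when c ≥ 13, that is t ≥ 12.5. With median m, the share is 2^(−12.5/m). Subtracting 2^(−55.5/m) gives the part that would occur by Day 56.

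| Assumed median (days) | Stops after Day 13 | Of all stops: after Day 13 but by Day 56 |
|---|---|---|
| 3 | 5.6% | 5.6% |
| 5 | 17.7% | 17.7% |
| 7 | 29.0% | 28.6% |
| 10 | 42.0% | 39.9% |
| 14 | 53.8% | 47.4% |

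In the last row the ordinal curve never reaches 50%, so the median is not estimable.

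**Effect on the log-rank test.** Simulated power, hazard ratio 2.0 (assumed), two-sided 0.05, 2000 replicates:

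| Control median, ventilated per arm | Exact, to Day 56 | Exact, to Day 14 | Ordinal, to Day 14 |
|---|---|---|---|
| 5 days, 10 | 0.327 | 0.322 | 0.319 |
| 5 days, 40 | 0.858 | 0.841 | 0.833 |
| 10 days, 10 | 0.315 | 0.264 | 0.261 |
| 10 days, 40 | 0.870 | 0.777 | 0.759 |

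The first step across each row is the Day 14 cut. It costs about 0.5 to 2 points at a median of 5 days and 5 to 9 points at 10 days. The second step is daily scoring, about 0 to 2 points. Each power has a standard error of about 1 point (√(0.3 × 0.7 / 2000) ≈ 0.010), so differences below one point should be read as roughly nil.

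**Scale.** Forty per arm would mean that every subject is ventilated, which is a ceiling. If 10% to 30% of the 120 were on positive pressure ventilation (an assumption), 12 to 36 subjects in all, or 4 to 12 per arm, would inform the endpoint.

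**The case against.** The strongest reply is that the choice is coherent and nearly harmless. The ordinal scale is the trial's primary instrument. Days of ventilator support is itself listed as an ordinal-scale parameter (Protocol 3.2, SAP 3.2), whereas time to ventilator cessation appears among the secondary objectives but is not itemised among the secondary endpoints. The rule is identical in all arms, and a near-uniform delay hardly changes the ordering of events, which is what the log-rank test uses. At 10 per arm, power is low whichever source is used. P-values are informational only (SAP 4.1). The worst-of-day rule also requires a ventilator-free day and shows death as its own category, while a raw stop time might be entered at death or at a short interruption.

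Most of this stands and keeps the point modest. It does not explain why times recorded for this endpoint are left out of its analysis, and it does not restore the tail after Day 13. The remarks on death and interruptions show what the new definition must contain.

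Some stronger readings are tempting but unsupported:

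- **A ventilated subject who leaves the ICU is falsely counted as a cessation.** The level's label pairs ventilation with an ICU stay, but the worked example in Protocol 6.3.9 classes a patient ventilated on the hospital floor as mechanically ventilated.
- **Late stops are dropped, or bias the comparison.** Those subjects stay in the analysis, right-censored at or before Day 14. Information is lost, but that is not in itself bias.
- **The recorded times go unused.** SAP 9.2.5 summarises hours on ventilation.
- **Stop times are known to exist through Day 56.** Protocol 6.3.3 gives no collection period. The healthcare items captured through the last visit are hospital stay, ICU stay and rehospitalisation; ventilation is not named.

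**Conclusion.** The point holds as a loss of precision on a secondary, unpowered analysis, and it is worth correcting because the correction is cheap. Under the SAP rule, times are whole days, the last countable stop is on Day 13, and recorded times run about 0.5 to 1.5 days late if infusion is at mid-Day 1 and the event is the first ventilator-free day.

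The truncation matters more than the daily scoring, and its importance depends on ventilation durations that the documents do not give. It is small if ventilation is short and moderate if it is long. The power figures rest on exponential times, no deaths and a hazard ratio of 2.0. They are illustrations and do not predict this trial's power. The gain from using stop times after Day 13 also depends on how long and how completely EDC records them.

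**What to change.** In SAP 9.2.4:

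- Define the event from the EDC stop date and time of ventilation, measured from infusion start and followed as far as stop times are recorded, up to Day 56. State the actual collection period.
- State that a stop at death is not a cessation, and how deaths enter the analysis.
- State that a stop followed by re-ventilation within a prespecified interval is not a cessation. This matters because the protocol's definition of positive pressure ventilation includes mask CPAP and BiPAP (Protocol 10.2).
- Keep the ordinal-based version as a sensitivity analysis, and name the score change that marks its event.

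List the derivation in SAP 16.1.

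The cost is SAP wording and extra programming, with no new data collection. The downside is reliance on complete EDC stop times, so their completeness should be checked before unblinding.

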#### **9.2.5 Healthcare resource utilization**

Descriptive statistics will be used to compare the total number of days in the hospital and/or ICU from admission to discharge, number of subjects requiring ICU admission post-randomization, overall number of days in the ICU, number of hours on ventilation, rehospitalization due to influenza A relapse/reinfection, the total number of days of oseltamivir therapy, and the total number of days to resumption of usual activities by treatment group.

Time (number of days) to resumption of usual activities will be determined from the VAS (scale ranged from 0 to 10, where 0 indicates subject is unable to perform any of his/her usual activities prior to influenza onset, and 10 indicates subject is able to fully perform all usual activities). Time to resumption of usual activities will be calculated as the difference between the first day the subject reports a score of 10 and Day 1. If a subject does not report a score of 10 by Day 14, a value of 14 will be used in the analysis. This evaluation will be performed using the MITT population. Additional analyses of VAS scores will reflect summaries of mean VAS scores by study day (up to Day 14), along with change from baseline and percent change from baseline will be generated; p-values will be based on ANOVA using rank transformation of VAS scores. VAS summaries will also be generated in the subsets of subjects with time from onset of symptoms to treatment < 72 hours or ≥ 72 hours. Mean VAS scores by study day along with standard deviations will be presented in figures, overall subjects and in the indicated subsets.

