  - Geographic region of enrollment
- Time to clinical response defined as resolution of at least 4 of 5 vital signs
  - Afebrile with core temperature ≤ 37.8°C, without use of antipyretics (oral ≤ 37.2°C)
  - Oxygen saturation ≥ 95% on room air without support or a return to pre-infection status, if pre-infection status was < 95%
  - Pulse rate ≤ 100/min
  - Systolic blood pressure ≥ 90 mm/Hg, without vasopressor use
  - Respiratory rate ≤ 24 beats per minute
- Clinical status ordinal scale mean area under curve for Days 1-7 and Days 1-14, using linear numeric scores for the ordinal categories.
- Comparison of clinical status ordinal scale scores for selected individual days (ie, Days 3, 4, 5, and 6)
- Comparison of clinical status ordinal scale scores using modified ordinal scale criteria (ie, pooling of selected severity criteria scores)
- Comparison of discrete ordinal scale parameters, including days of ventilator support, days in intensive care, and duration of hospitalization
- Number of days to resumption of usual activities
- All-cause and attributable mortality rates at Day 14, 28 and 56
- Total number of days in hospital and/or intensive care unit (ICU) from admission to discharge and rate of rehospitalization due to influenza A relapse/complication
- The incidence, severity, and duration of signs and symptoms of influenza-like illness as assessed by the FluPRO Questionnaire (see Appendix 16.3.1)
- The percentage of subjects with new bacterial pneumonia/superinfection

January 17, 2019

- The percentage of subjects with influenza-related complications
- VIS410 pharmacokinetic (PK) parameters in serum
- Titer of anti-VIS410 antibody positive samples
- Genotypic and/or phenotypic assessment to determine the emergence of VIS410 and oseltamivir-resistant viruses

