## 4.2 Missing Data Conventions

Partial and missing AE and concomitant medication dates will be imputed with maximum conservatism. If the onset date is missing or partial, the date will be compared as far as possible with the date of first dose of study medication. If no month is present and it is in the same year as the date of first treatment, or the year and month are the same as the first treatment date, the onset date will be imputed as the date of first treatment. Otherwise it will be imputed as 01 January in the available year, or the first day of the month and year available. End dates will be imputed as 31 December in the available year, or the last day of the available month and year collected. Partial dates will be presented in listings, along with classifications of TEAE for AEs or Prior/Concomitant/Both for medications.

Missing data will generally be left as missing, except for partial and missing AE and concomitant medication dates. Special cases, e.g. below the limit of quantification, will be described in the sections that describe the specific parameter's analysis.

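### Hospital, ICU and ventilation totals in SAP 9.2.5 have no rule for deaths, so early death can make an arm look better; this is cheap to repair

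*SAP*

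**What the plan says.** SAP 9.2.5 describes these quantities by treatment group: the "total number of days in the hospital and/or ICU from admission to discharge", and then "overall number of days in the ICU, number of hours on ventilation". The method is descriptive ("Descriptive statistics will be used to compare the total number of days in the hospital"), and no test is named for these totals. SAP 3.2 gives the first of them secondary-endpoint status with the same start and end points: "Total number of days in hospital and/or intensive care unit (ICU) from admission to discharge".

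Two neighbouring items in 9.2.5 are anchored to the trial. ICU admission is restricted ("number of subjects requiring ICU admission post-randomization"), and time to usual activities is "the difference between the first day the subject reports a score of 10 and Day 1", with 14 assigned to subjects who have not reached a score of 10 by Day 14. The day and hour totals have no Day 1 start, no fixed window and no rule for deaths.

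The general convention in SAP 4.2 does not supply one: "Missing data will generally be left as missing, except for partial and missing AE and concomitant medication dates".

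SAP 3.2 also lists a related but separate item, "Comparison of discrete ordinal scale parameters, including days of ventilator support, days in intensive care, and duration of hospitalization". SAP 9.2.1 implements part of it, counting days through Day 14 spent dead, on a ventilator or in ICU.

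**The concern.** A length of stay ends for two opposite reasons: the patient recovers, or the patient dies. A total that does not separate them treats a short stay as good in both cases. In a population where death is the worst category of the primary endpoint, an arm with more early deaths can show fewer hospital, ICU and ventilation days with no faster recovery.

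This matters because the study exists to choose Phase 3 endpoints (protocol 10.1, SAP 2.2). SAP 2.4.2 says the secondary objectives, including healthcare resource utilization, will be assessed in four treatment pairings. An endpoint whose direction depends on when deaths occur is a poor candidate.

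A lesser issue is the start point. Hospital days before infusion cannot respond to treatment. The current exclusion criteria set no limit on prior hospital stay, and symptoms may have begun up to 5 days before infusion.

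**Working it through.** The plan gives no assumed stay, effect or power for these totals, so there is no figure to reproduce. What follows is illustration.

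**Inputs**
- p, early mortality. Protocol 1.1 says 10% to 44% of hospitalised patients need intensive care and 25% to 50% of those die. That implies 0.10 × 0.25 = 2.5% to 0.44 × 0.50 = 22%. This is a background range, not an expected difference between arms. A 5% against 10% contrast is added as a smaller assumed gap.
- S, survivors' stay: 7, 9 or 12 days (assumed, equal in both arms).
- D, day of death: 3, 4 or 5 (assumed).

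**Reading 1: the count stops at death.** Mean raw stay = pD + (1 − p)S. The higher-mortality arm is therefore shorter by (p₂ − p₁)(S − D).

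**Death-penalised version.** Mean days alive and out of hospital to Day 28, deaths = 0, is (1 − p)(28 − S). The higher-mortality arm loses (p₂ − p₁)(28 − S).

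| S, D | Raw stay shorter by, 10% vs 5% | Raw stay shorter by, 22% vs 2.5% | Free days lost, 10% vs 5% | Free days lost, 22% vs 2.5% |
|---|---|---|---|---|
| 7, 3 | 0.05 × 4 = 0.20 | 0.195 × 4 = 0.78 | 0.05 × 21 = 1.05 | 0.195 × 21 = 4.1 |
| 9, 4 | 0.05 × 5 = 0.25 | 0.195 × 5 = 0.975 | 0.05 × 19 = 0.95 | 0.195 × 19 = 3.7 |
| 12, 5 | 0.05 × 7 = 0.35 | 0.195 × 7 = 1.37 | 0.05 × 16 = 0.80 | 0.195 × 16 = 3.1 |

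Survivors recover identically, yet the raw total favours the arm with more deaths in every row. The penalised count goes against it. One extra early death in an arm of 40 lowers the raw mean by (S − D)/40, which is 0.10 to 0.175 day.

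**Reading 2: discharge is missing for a death.** The subject leaves the summary and both arms average S whatever the mortality. The comparison is then among survivors only, not between the randomised groups.

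**Late death.** If D exceeds S the sign flips. With S = 9 and an assumed death at day 20, 10% vs 5% gives 0.05 × (9 − 20) = −0.55, so the higher-mortality arm looks 0.55 day longer.

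**Days before Day 1.** Assume the pre-infusion stay is uniform on 0 to 5 days, with variance 25/12 = 2.08. SD inflation is √(SD² + 2.08)/SD. For a post-Day 1 SD of 3, 5, 7 or 10 days this is 1.110, 1.041, 1.021 or 1.010. For a uniform 0 to 2 days (variance 0.33) it is at most √9.33/3 = 1.018.

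**SAP 9.2.1.** Take a subject in ICU who dies on Day 4. Under the worst-status-of-the-day rule, with death carried forward, there are 3 ICU days and 11 death days. If death days are added in, the count is 14, worse than a survivor with 9 ICU days. If they are shown separately, the ICU count is 3, better than that survivor. Section 9.2.1 does not say which applies. Its text also omits hospital days, and the carry-forward rule in SAP 9.1 is written only for deaths before Day 7.

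**The case against.** The case for leaving the plan alone has real substance.

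- The section concerns resource use, where days actually consumed are a legitimate quantity. This stands, and is why the raw totals should stay.
- The totals are descriptive in a study declared exploratory and unpowered. This largely stands and limits the harm. It does not repair the definition, and the protocol synopsis promises p-values on secondary endpoints to inform Phase 3 choices.
- A reader might infer that the trial could mistake excess mortality for benefit. The documents do not support that. Death is the worst level of the primary scale and is analysed as its own secondary endpoint. All-cause mortality is evaluated at Days 14, 28 and 56, with tables in the Safety and MITT populations.
- A reader might also infer that every day count in the plan ignores death. It does not: 9.2.1 runs over Days 1 to 14 and lists death as a severe state. What remains is how its counts combine and the absence of hospital days.
- It is tempting to say ventilation is counted from admission. That start point is written only for the hospital and/or ICU total; for ventilation hours none is stated.
- Pre-infusion days might be read as a bias. They precede allocation and are balanced in expectation, so they add noise only.
- Exclusion criterion 10 removes subjects judged likely to die within 48 hours, so very early deaths should be fewer. This is fair, and favours the smaller figures above.

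**Conclusion.** The gap is real but limited. The totals in SAP 9.2.5, and the matching hospital/ICU endpoint in 3.2, have no rule for subjects who die. Early death either shortens the total or removes the subject, and the comparison can point the wrong way.

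The size depends on assumed stays, death days and mortality. At 10% against 5% early mortality it is 0.2 to 0.35 day. The 0.8 to 1.4 day range needs the two extremes of a background range set against each other, and should not be read as an expected distortion. The direction is not fixed either, since late deaths lengthen the total.

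Starting the hospital/ICU count at admission adds about 1% to 11% to the SD for an assumed 0 to 5 day pre-infusion stay, and no bias. SAP 9.2.1 is a partial counterweight for ICU and ventilator days. Overall this is a cheap improvement.

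**What to change.** 1. In SAP 9.2.5, keep the raw totals and label them descriptive resource use.
2. Add three derived variables counted from Day 1 through Day 28: days alive and out of hospital, days alive and out of ICU, and days alive and off ventilation. Set each to 0 for a subject who dies by Day 28. Compare arms with the rank-based ANOVA already used in 9.2.5 and 9.2.6.
3. In SAP 9.2.1, state that days after death count as days in the severe state, for any death through Day 14.

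The data are already collected: hospital and ICU dates (protocol 6.3.5), ventilation start and stop times (protocol 6.3.3), and deaths (SAP 9.2.7). The cost is SAP wording and one derivation. The downside is one more set of derived variables in a plan that already has many.
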